8.3. EXPLORATORY EFFICACY ENDPOINTS AND ANALYSES

8.3.1. Computerized Neuropsychological Test Battery Episodic Memory Domain Composite Score

The episodic memory domain of the cNTB is a composite score of the ISLT (immediate and delayed recall) and OCL tests. Calculation of the episodic memory domain composite score will be carried out by calculating for each given patient at each given assessment the z score as described in [Section 8.1](#). A minimum of 2 out of 3 valid test scores are required for the calculation of the mean of the available z-scores composing the domain composite score.

The cNTB episodic memory domain global scores and changes from baseline will be summarized (by treatment) at each visit. Change in cNTB episodic memory domain composite scores from baseline to Week 26 (Visit 5) will be analyzed using an MMRM model utilizing all baseline and postbaseline data to assess any differences in treatment effects over time. The model will include fixed effects of treatment, study site, visit, and treatment by visit interaction, with baseline score, age, gender and ApoE4 as covariates, and a baseline by visit interaction. The global treatment effect estimates will be reported, with 95% confidence intervals and *P* values. Baseline will be the last non-missing observation at Visit 2 or before. The adjusted mean difference between treatments versus placebo will be presented along with the standard error and a 95% confidence interval.

These analyses will be performed using PROC MIXED in SAS, and adjusted means will be obtained by using the LSMEANS statement.

A supportive efficacy analysis will be carried out using an ANCOVA method where the change in cNTB episodic memory domain scores from baseline to Week 4 (Visit 3), Week 13 (Visit 4) Week 26 (Visit 5) will be the outcome variable and treatment group and study site will be main effects. The cNTB episodic memory domain composite scores at baseline, age, gender and ApoE4 will be included as covariates. Multiple imputations for missing values (at the level of the composite score, not at the level of the individual tests) will take place using the pattern mixture model approach, as described in [Section 8.1](#). The standard error of the change from baseline will also be included. The adjusted mean difference between treatments versus placebo will be presented along with the standard error and a 95% confidence interval.

8.3.2. Computerized Neuropsychological Test Battery Attention Domain Composite Score

The attention domain of the cNTB is a composite score of the IDN and DET tests. Calculation of the attention domain composite score will be carried out by calculating for each given patient at each given assessment the z score as described in [Section 8.1](#). Two valid test scores are required for the calculation of the mean of the available z-scores composing the domain composite score.

The cNTB attention domain global scores and changes from baseline will be summarized (by treatment) at each visit. Change in cNTB attention domain scores from baseline over Week 26 will be analyzed using a MMRM model utilizing all baseline and postbaseline data to assess any differences in treatment effects over time. The model will include fixed effects of treatment, study site, visit, and treatment by visit interaction, with baseline score, age, gender and ApoE4 as covariates, and a baseline by visit interaction. The global treatment effect estimates will be reported, with 95% confidence intervals and *P* values. Baseline will be the last non-missing observation at Visit 2 or before. The adjusted mean difference between treatments versus placebo will be presented along with the standard error and a 95% confidence interval.

These analyses will be performed using PROC MIXED in SAS, and adjusted means will be obtained by using the LSMEANS statement.

A supportive efficacy analysis will be carried out using an ANCOVA method where the change in cNTB attention domain composite scores from baseline to Week 4 (Visit 3), Week 13 (Visit 4) and Week 26 (Visit 5) will be the outcome variable and treatment group and study site will be main effects. cNTB attention domain composite scores at baseline, age, gender and ApoE4 will be included as covariates. Multiple imputations for missing values (at the level of the composite score, not at the level of the individual tests) will take place using the pattern mixture model approach, as described in [Section 8.1](#). The standard error of the change from baseline will also be included. The adjusted mean difference between treatments versus placebo will be presented along with the standard error and a 95% confidence interval.

8.3.3. Executive Function Domain Composite Score

The executive function domain is a composite score of the OBK, COWAT and CFT tests. Calculation of the executive function domain composite score will be carried out by calculating for each given patient at each given assessment the z score as described in [Section 8.1](#). A minimum of 2 out of 3 valid test scores are required for the calculation of the mean of the available z-scores composing the domain composite score.

The cNTB executive function domain global scores and changes from baseline will be summarized (by treatment) at each visit. Change in cNTB executive function domain scores from baseline over Week 26 will be analyzed using a MMRM model utilizing all baseline and postbaseline data to assess any differences in treatment effects over time. The model will include fixed effects of treatment, study site, visit, and treatment by visit interaction, with baseline score, age, gender and ApoE4 as covariates, and a baseline by visit interaction. The global treatment effect estimates will be reported, with 95% confidence intervals and *P* values. Baseline will be the last non-missing observation at Visit 2 or before. The adjusted mean difference between treatments versus placebo will be presented along with the standard error and a 95% confidence interval.

These analyses will be performed using PROC MIXED in SAS, and adjusted means will be obtained by using the LSMEANS statement.

A supportive efficacy analysis will be carried out using an ANCOVA method where the change in cNTB executive function domain scores from baseline to Week 4 (Visit 3), Week 13 (Visit 4) and Week 26 (Visit 5) will be the outcome variable and treatment group and study site will be main effects. The cNTB executive function domain scores at baseline, age, gender and ApoE4 will be included as covariates. Multiple imputations for missing values (at the level of the composite score, not at the level of the individual tests) will take place using the pattern mixture model approach, as described in [Section 8.1](#). The standard error of the change from baseline will also be included. No imputation for missing values at Week 26 will take place. The adjusted mean difference between treatments versus placebo will be presented along with the standard error and a 95% confidence interval.

8.3.4. Mini Mental State Examination

The MMSE is a brief assessment instrument used to assess cognitive function in elderly patients. The instrument is divided into 2 sections. The first section measures orientation, memory, and attention; the maximum score is 21. The second section tests the ability of the patient to name objects, follow verbal and written commands, write a sentence, and copy figures: the maximum score is 9. The scoring range for the MMSE is 0-30.

Change in MMSE global scores from baseline to Week 26 (Visit 5) will be analyzed using an ANCOVA method where the change in MMSE scores from baseline to Week 26 will be the outcome variable and treatment group and study site will be main effects. MMSE scores at baseline, age, gender and ApoE4 will be included as covariates. Baseline will be the last non-missing observation at Screening (Visit 1). The standard error of the change from baseline will also be included. Multiple imputations for missing values will take place using the pattern mixture model approach, as described in [Section 8.1](#). The adjusted mean difference between treatments versus placebo will be presented along with the standard error and a 95% confidence interval.

8.3.5. Individual Computerized and Paper-Based Neuropsychological Test Battery Score

The individual z-scores of the cNTB include ISLT (immediate and delayed recall), OCL, IDN, DET, OBK, and paper-based COWAT and CFT.

Change in the individual NTB scores from baseline to Week 26 (Visit 5) will be analyzed using a MMRM model utilizing all baseline and postbaseline data to assess any differences in treatment effects over time. The model shall include fixed effects of treatment, study site, visit, and treatment by visit interaction, with baseline score, age, gender and ApoE4 as covariates, and a baseline by visit interaction. The global treatment effect estimates will be reported, with 95% confidence intervals and

P values. Baseline will be the last non-missing observation at Visit 2 or before. The adjusted mean difference between treatments versus placebo will be presented along with the standard error and a 95% confidence interval.

These analyses will be performed using PROC MIXED in SAS, and adjusted means will be obtained by using the LSMEANS statement.

As supportive analysis for the change in the individual NTB scores from baseline to Week 4 (Visit 3), Week 13 (Visit 4) and Week 26 (Visit 5) will be analyzed using an ANCOVA method, where the change in individual NTB scores from baseline (Visit 2) to Week 26 (Visit 5) will be the outcome variable and treatment group and study site will be main effects. The individual NTB scores at baseline, age, gender and ApoE4 will be included as covariates. The standard error of the change from baseline will also be included. Multiple imputations for missing values will take place using the pattern mixture model approach, as described in [Section 8.1](#). The adjusted mean difference between treatments versus placebo will be presented along with the standard error and a 95% confidence interval.

8.3.6. Neuropsychiatric Inventory

The NPI scale consists of 12 domains that are rated for both frequency (range 1-4) and severity (range 1-3). A composite score for each domain is calculated (frequency × severity), which ranges from 1 to 12. There is a leading question for each item. If the symptom is not present, then the frequency, severity, and distress scores are not completed. In this case the score is 0 for the item. The sum of the composite scores yields the NPI-12 total score (range 0-144). A negative change in score indicates an improvement from baseline (symptom reduction).

Change in the NPI individual items and global scores from baseline to Week 26 (Visit 5) will be analyzed using an ANCOVA method, where the change in the NPI scores from baseline to Week 26 will be the outcome variable and treatment group and study site will be main effects. The NPI scores at baseline, age, gender, and ApoE4 will be included as covariates. Baseline will be the last non-missing observation at Visit 2. The standard error of the change from baseline will also be included. Multiple imputations for missing values will take place using the pattern mixture model approach, as described in [Section 8.1](#). The adjusted mean difference between treatments versus placebo will be presented along with the standard error and a 95% confidence interval.

The NPI-10 total score (range 0-120) will also be calculated by removing the sleep and appetite and eating domains. This will be summarized and analyzed as per the NPI-12 score. The distress score shall be listed only.

8.3.7. Pittsburgh Sleep Quality Index

The PSQI is an effective instrument used to measure the quality and patterns of sleep in older adults. It differentiates “poor” from “good” sleep by measuring 7 areas

(components): subjective sleep quality, sleep latency, sleep duration, habitual sleep efficiency, sleep disturbances, use of sleeping medication, and daytime dysfunction over the last month. The patient self-rates each of these 7 areas of sleep. Scoring of answers is based on a 0 to 3 scale, where a score of 3 reflects the negative extreme on the Likert Scale. A global sum of 5 or greater indicates a “poor” sleeper.

Change in the PSQI, for each of the 7 individual components, questions 2 and 4, and the global scores from baseline will be summarized (by treatment) at each visit. Change in PSQI scores from baseline to Week 26 will be analyzed using a MMRM model utilizing all baseline and postbaseline data to assess any differences in treatment effects over time. The model will include fixed effects of treatment, study site, visit, and treatment by visit interaction, with baseline score, age, gender and ApoE4 as covariates, and a baseline by visit interaction. The global treatment effect estimates will be reported, with 95% confidence intervals and *P* values. Baseline will be the last non-missing observation at Visit 2. The adjusted mean difference between treatments versus placebo will be presented along with the standard error and a 95% confidence interval.

These analyses will be performed using PROC MIXED in SAS, and adjusted means will be obtained by using the LSMEANS statement.

As supportive analysis for the change in PSQI scores (individual components and global) from baseline to Week 4 (Visit 3), Week 13 (Visit 4) and Week 26 (Visit 5) will be analyzed using an ANCOVA method where the change in the PSQI scores from baseline to Week 4, Week 13, or Week 26 will be the outcome variable and treatment group and study site will be main effects. The PSQI scores at baseline, age, gender, and ApoE4 will be included as covariates. Multiple imputations for missing values will take place using the pattern mixture model approach, as described in [Section 8.1](#). The standard error of the change from baseline will also be included. The adjusted mean difference between treatments versus placebo will be presented along with the standard error and a 95% confidence interval.

8.3.8. Alzheimer’s Disease Assessment Scale Cognitive 13, 12 and 11 Subscale

The ADAS-cog13, ADAS-cog12 and ADAS-cog11 scores and changes from baseline will be summarized (by treatment) separately at each visit. Change in ADAS-cog13, ADAS-cog12 and ADAS-cog11 scores from baseline to Week 26 (Visit 5) will be analyzed separately using a MMRM model utilizing all baseline and postbaseline data to assess any differences in treatment effects over time. The model will include fixed effects of treatment, study site, visit, and treatment by visit interaction, with baseline score as a covariate, and a baseline by visit interaction. The global treatment effect estimates will be reported, with 95% confidence intervals and *P* values. Baseline will be the last non-missing observation at Visit 2. The adjusted mean difference between treatments versus placebo will be presented along with the standard error and a 95% confidence interval.

These analyses will be performed using PROC MIXED in SAS, and adjusted means will be obtained by using the LSMEANS statement.

As supportive analysis for the change in ADAS-cog 11, 12 and 13 scores from baseline to Week 13 (Visit 4) and Week 26 (Visit 5) will be analyzed using an ANCOVA method, where the change in ADAS-cog 11, 12 and 13 scores from baseline to Week 26 will be the outcome variable and treatment group and study site will be main effects. The ADAS-cog 11, 12 and 13 scores at baseline, age, gender, and ApoE4 will be included as covariates. Multiple imputations for missing values will take place using the pattern mixture model approach, as described in [Section 8.1](#). The standard error of the change from baseline will also be included. The adjusted mean difference between treatments versus placebo will be presented along with the standard error and a 95% confidence interval.

8.3.9. Computerized Neuropsychological Test Battery Global Composite Score without Paper-Based Components

The cNTB global composite score contains both computerized and paper-based (CFT and COWAT) scores. As an exploratory analysis, the analyses on the cNTB global composite score shall be repeated with the paper-based components removed.

Change in cNTB global composite scores from baseline to Week 4 (Visit 3), from baseline to Week 13 (Visit 4), and from baseline to Week 26 (Visit 5) will be analyzed using a MMRM model utilizing all baseline and postbaseline data to assess any differences in treatment effects over time. The model will include fixed effects of treatment, study site, visit, and treatment by visit interaction, with baseline score, age, gender and ApoE4 as covariates, and a baseline by visit interaction. The global treatment effect estimates will be reported, with 95% confidence intervals and *P* values. Baseline will be the last non-missing observation at Visit 2 or before. The standard error of the change from baseline will also be included. The adjusted mean difference between treatments versus placebo will be presented along with the standard error and a 95% confidence interval.

These analyses will be performed using PROC MIXED in SAS, and adjusted means will be obtained by using the LSMEANS statement.

A supportive efficacy analysis will be carried out using an ANCOVA method where the change in cNTB global composite scores from baseline to Week 4 (Visit 3), Week 13 (Visit 4), and Week 26 (Visit 5) will be the outcome variable and treatment group and study site will be main effects. cNTB global composite scores at baseline, age, gender, and ApoE4 will be included as covariates. The standard error of the change from baseline will also be included. Multiple imputation for missing values (at the level of the composite score, not at the level of the individual tests) will take place using the pattern mixture model approach, as described in [Section 8.1](#). The adjusted mean difference between treatments versus placebo will be presented along with the standard error and a 95% confidence interval. Global composite scores will be

calculated as described in [Section 8.1](#), but with the removal of the paper-based CFT and COWAT components.

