6.3. MISSING DATA

In cases of missing baseline data for cNTB tests, the pre-baseline value will be taken for analysis. If the pre-baseline value is missing as well, values from Screening will be taken and used for analysis as baseline. In cases where the baseline value for COWAT, CFT and ADAS-cog14 are missing, values obtained at Screening will be taken and used for analysis.

Pattern mixture model imputation will be used to treat missing data for all analyses of covariance (ANCOVA) as described in [Section 8.1](#). In the case of cNTB composite scores the imputation will be carried out at the level of the composite score, not at the level of individual tests.

Missing data for AEs where toxicity and relationship to study drug are missing will be treated as described in [Section 9.3](#).

Missing or partial dates for concomitant medications and adverse events will be treated as described in Sections [7.6](#) and [9.3](#) respectively.

No other imputation of missing data shall be performed.

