8.2.3. Alzheimer's Disease Assessment Scale Cognitive 14 Subscale

The ADAS-cog consists of 11 tasks measuring the disturbances of memory, language, praxis, attention, and other cognitive abilities that are often referred to as the core symptoms of AD. The test comprises 11 items summed to a total score ranging from 0 to 70, with lower scores indicating less severe impairment. A negative change indicates an improvement from baseline. The addition of delayed recall, number cancellation, and maze tasks - and thus turning ADAS-cog into a 12-, 13-, and 14-item scale, respectively - has increased the ability to detect changes in patients in the early stages of the disease.

The ADAS-cog14 global scores and changes from baseline will be summarized (by treatment) at each visit. Change in ADAS-cog14 scores from baseline over Week 26 (Visit 5) will be analyzed using a MMRM model utilizing all baseline and postbaseline data to assess any differences in treatment effects over time. The model will include fixed effects of treatment, study site, visit, and treatment by visit interaction, with baseline score, age, gender and ApoE4 as covariates, and a baseline by visit interaction. The global treatment effect estimates will be reported, with 95% confidence intervals and *P* values. Baseline will be the last non-missing observation at Visit 2 or before. The adjusted mean difference between treatments versus placebo will be presented along with the standard error and a 95% confidence interval.

These analyses will be performed using PROC MIXED in SAS, and adjusted means will be obtained by using the LSMEANS statement.

An effect size calculation will be performed, where Cohen's *d* effect size will be calculated on the adjusted mean difference of change from baseline of treatment versus placebo. The effect size will be derived as the adjusted mean difference divided by the pooled standard deviation.

A supportive analysis will be carried out using an ANCOVA method where the change in ADAS-cog14 scores from baseline to Week 13 (Visit 4) and Week 26 (Visit 5) will be the outcome variable and treatment group and study site will be main effects. The ADAS-cog14 scores at baseline, age, gender and ApoE4 will be included as covariates. Baseline will be the last non-missing observation at Visit 2 or before. Multiple imputations for

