10. CHANGE FROM ANALYSIS PLANNED IN PROTOCOL

Sample size and statistical power: In order to meet piromelatine drug development program timelines it has been decided to reduce the sample size for the ReCOGNITION study from 500 to 400 evaluable subjects. This reduction results from changing the originally highly powered study at 88% to 80%, while keeping the effect size (0.35) based on which the sample size was calculated. This is still an acceptable power in clinical trials which Neurim believes is appropriate to confirm the potential efficacy of piromelatine.

Primary endpoint: Version 7 of the protocol included the addition of COWAT and CFT to executive function domain of the cNTB. These two tests should have been included also in the global composite score. The rules for a valid global composite score will include now over 8 tests (ISLT immediate and delayed, OCL, IDN, DET, OBK, COWAT and CFT) instead of 6, of which the executive function domain will include 3 tests (OBK, COWAT and CFT).

Primary and secondary statistical analysis: For all endpoints the order was reversed; MMRM will be used as the primary endpoint, while ANCOVA will be used as the secondary analysis.

Secondary and exploratory analysis: cNTB attention, cNTB episodic and executive function domains have been moved from secondary to exploratory efficacy endpoints.

Co-variates: Age, gender, and ApoE4 will be used as co-variates for the MMRM and ANCOVA.

Imputations: The pattern mixture model approach will be used for the ANCOVA in cases of missing values as described in [Section 8.1](#).

Analysis of the CGIC endpoint: The protocol states that the ANCOVA method will be used to analyze the change from baseline between the treatment groups. As there is no baseline result recorded in the CRF, this method is not appropriate for this endpoint. The difference between the treatment groups will instead be evaluated by means of the van Elteren version of the Cochran-Mantel-Haenszel test.

MMSE: Section 17.3.4 of the protocol states that MMSE will be analyzed using an ANCOVA. This analysis will be performed on the global scores.

NPI: Section 17.3.4 of the protocol states that NPI will be analyzed using an ANCOVA. This analysis will be performed on individual items and the global score of 10 and 12 items.

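### The exploratory ADAS-cog13/12/11 MMRM omits age, gender and ApoE4, against SAP Section 10, and words its baseline more narrowly than ADAS-cog14

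*SAP*

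**What the plan says.** **Covariates.** In Section 8.3.8 the MMRM for the three shorter ADAS-cog versions is fitted "with baseline score as a covariate, and a baseline by visit interaction". The supportive ANCOVA in the same section is fuller: "The ADAS-cog 11, 12 and 13 scores at baseline, age, gender, and ApoE4 will be included as covariates". For ADAS-cog14, Section 8.2.3 has the MMRM "with baseline score, age, gender and ApoE4 as covariates, and a baseline by visit interaction". Section 10, which records departures from the protocol and is current plan text, states: "Age, gender, and ApoE4 will be used as co-variates for the MMRM and ANCOVA".

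**Baseline.** Section 8.3.8 says "Baseline will be the last non-missing observation at Visit 2" and stops there. Section 8.2.3 says "Baseline will be the last non-missing observation at Visit 2 or before". Section 6.3 adds: "In cases where the baseline value for COWAT, CFT and ADAS-cog14 are missing, values obtained at Screening will be taken and used for analysis". It does not mention versions 13, 12 or 11. The general definition in Section 6.2 allows Screening to stand in for Week 0, but only where nothing else is specified.

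**Genotype.** Sections 7.5 and 9.4 describe ApoE4 genotyping as optional. Section 6.3 closes by ruling out any imputation beyond the kinds it lists, and a missing genotype is not among them.

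**The concern.** A programmer cannot follow both Section 8.3.8 and Section 10 when building this model. Section 8.3.8 gives no reason for a reduced covariate set, and its own ANCOVA uses the full set, so it reads as an update that was missed when the three covariates were added elsewhere. If the conflict is not settled before database lock, the choice could be made after unblinding.

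The baseline wording creates a second, independent split. Section 8.2.3 describes the 12-, 13- and 14-item scales as extensions of the 11-item test, so all four scores share their core items. Readers will naturally look at the four results side by side. Differences in covariates, and possibly in patients, would then be mixed with differences in items. In addition, a gap between the 13/12/11 MMRM and its supportive ANCOVA could not be put down to the handling of missing data alone, because the covariates differ too.

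**Working it through.** The main check is a comparison of text. The SAP gives no figure to reproduce on this point.

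**Step 1: covariates across the MMRMs in Section 8.**

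| SAP section | Age, gender, ApoE4 in MMRM? |
|---|---|
| 8.1, 8.2.2, 8.2.3, 8.2.4 | yes |
| 8.3.1, 8.3.2, 8.3.3, 8.3.5, 8.3.7, 8.3.9 | yes |
| 8.3.8 | no |

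Ten include them and one does not. Section 10 makes no exception for that one, so there is a contradiction.

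**Step 2: baseline.** Section 6.2 gives way to any section that specifies otherwise, and 8.3.8 does specify Visit 2. The Screening substitution in 6.3 ("values obtained at Screening will be taken and used for analysis") is tied to COWAT, CFT and ADAS-cog14. On a strict reading, a patient with a Screening ADAS-cog but none at Visit 2 has a baseline for cog14 and none for cog11-13. Section 10 says nothing about baseline, so this is a separate inconsistency between 8.3.8 and 8.2.3 with 6.3.

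**Step 3: precision lost by omitting the covariates.** If they explain a share R² of residual variance, omitting them multiplies the standard error by 1/√(1 − R²). The SAP gives no R²; 2-5% is an assumption.
- R² = 0.02: 1/√0.98 = 1.010
- R² = 0.05: 1/√0.95 = 1.026

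**Step 4: precision lost by adding ApoE4 with complete cases only.** PROC MIXED leaves out records with a missing covariate. If a share m of patients has no genotype, the standard error is multiplied by about 1/√(1 − m). The SAP gives no m; 10-30% is an assumption. The base of 400 is the evaluable number in Section 10.
- m = 0.10: 40 of 400 lost, 1/√0.90 = 1.054
- m = 0.30: 120 of 400 lost, 1/√0.70 = 1.195

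**Step 5: the two together.** Adding the covariates with complete-case fitting changes the standard error by √[(1 − R²)/(1 − m)], which is above 1 whenever m exceeds R².
- Smallest net loss in these ranges: √(0.95/0.90) = 1.027
- Largest: √(0.98/0.70) = 1.183

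Under these assumptions, copying the 8.2.3 covariates into 8.3.8 without a rule for missing genotype would make the estimates less precise. The rule has to be part of the fix.

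**The case against.** The strongest reply is that this matters little. Versions 13, 12 and 11 are exploratory (Sections 3.3 and 4.3), a covariate-adjusted ANCOVA at Weeks 13 and 26 is already planned for them, and the assumed precision cost is 1-3%. All of that stands and limits the weight of the point. It does not remove the contradiction.

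On baseline, the same Visit 2 wording is used for ADCS-ADL, NPI and PSQI, so it is not peculiar to 8.3.8. The 6.3 fallback for ADAS-cog14 could also be meant to cover the shorter scores contained in it. That is a fair reading. The text does not say so, however, and the loss of patients follows only from the strict reading.

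A reader might infer three stronger things that the SAP does not support:
- **That the 13/12/11 MMRM uses the whole FAS while cog14 uses a fraction of it.** FAS membership (Section 5.3) rests on cNTB, which has a Week 4 assessment. ADAS-cog is analysed only at Weeks 13 and 26, so a patient who leaves after Week 4 can be in the FAS with no post-baseline ADAS-cog.
- **That a planned comparison between versions is spoiled.** Section 8.3.8 analyses each version separately and specifies no contrast between them. Even under identical models, the patient sets could differ if one of the added tasks is missing.
- **That both differences contradict Section 10.** Only the covariate omission does.

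**Conclusion.** The covariate omission is a definite contradiction: 8.3.8 conflicts with Section 10, with its own ANCOVA and with the ten other MMRMs written out in Section 8. The narrower baseline is a real difference in wording from ADAS-cog14. Whether it removes patients depends on a strict reading of 8.3.8.

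The consequence is limited to exploratory results; no primary or secondary analysis changes because of either inconsistency. The SAP does not give the number of patients without a genotype or with only a Screening ADAS-cog, so the number affected cannot be stated. The percentages above are illustrations on assumed ranges. The correction is worth making before database lock because it is cheap and removes a choice that the text now leaves open.

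**What to change.** - In 8.3.8, add age, gender and ApoE4 to the MMRM, as in 8.2.3.
- In 8.3.8, define baseline as the last available ADAS-cog value at or before Visit 2, as in 8.2.3, and add ADAS-cog13, 12 and 11 to the Screening fallback in 6.3.
- State how a missing genotype is handled in every model that uses ApoE4, so that ungenotyped patients are kept, for example with a separate 'not genotyped' category. The SAP has no such rule now. It would also apply to the models in 8.1 and 8.2, and should be written once for all of them. The subgroup analysis in 8.3.11 can stay restricted to patients who consented to genotyping.
- If the baseline-only model is intended, Section 10 should name it as an exception and give the reason.

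The cost is SAP wording and minor programming; the variables are already in the plan.
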